3.1 Hypothesis

Hypothesis 1: Clinicians' ratings of MBC implementation outcomes will increase following implementation strategies provided as compared to ratings during the baseline period. (Primary Objective)

Hypothesis 2: MBC fidelity (per MBC feedback system review) and use (per clinician self-report) will increase following implementation strategies provided as compared to ratings during the baseline period, with documentation of measure collection more prevalent than documentation of discussing progress or changing the treatment plan in accordance with measures. (Primary Objective)

Hypothesis 3: MBC fidelity and use will be positively associated with engagement and mental health symptom and functioning progress over time. (Secondary Objective)

Although underpowered to establish outcomes as a result of strategies applied with certainty, this pilot will provide mentored research experience and preliminary data for planning a future large-scale hybrid trial.

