4.1.1 General Design Description

A clustered, multiple-baseline design will be used to examine the impact of the implementation support condition on clinicians' fidelity, use and ratings of MBC appropriateness, acceptability and fidelity. Approximately 50 SMH clinicians will be recruited to participate from two school districts. All clinicians will receive the same implementation supports; there is no random assignment to condition. Following an initial control period of at least 1 month, school districts will start receiving implementation supports. During the initial control period, baseline MBC use, attitudes, acceptability, feasibility and appropriateness (per clinician self-report) will be collected, as well as needs assessment data from clinician surveys to inform necessary adjustments to the implementation supports. Baseline engagement and student outcomes will be collected after initial clinician training session. MBC implementation outcomes (i.e., MBC use, attitudes, acceptability, appropriateness, and feasibility), engagement and student outcomes will be collected at 3-month and 6-month follow-up during intervention supports, plus a 9-month follow-up interval. This allows clinicians in the two school districts to be compared to each other and to their own baseline. The primary comparison is pre-post ratings of implementation outcomes for all N=50 clinicians. The secondary comparisons are pre-post ratings of engagement and student outcomes, and between-agency differences.

Study Date Range and Duration

This study is expected to last approximately one calendar year from recruitment to follow-up, aligned with the 2021-2022 and 2022-23 academic years as the participating sites are school districts. Clinicians will start training and consultation in the fall of 2021 or 2022 and parents/guardians will be recruited in the fall of 2021 or 2022. Data collection will occur at baseline, 3 months, 6 months and 9 months.

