4.2.2 Secondary and Exploratory Outcome Variables

The secondary objective of this study is to examine effectiveness outcomes. **Effectiveness outcomes** of MBC will be measured using actual scores on the SRS and ORS, as documented in the student's service record. The SRS and ORS are part of the Partners for Change Outcome Management System (PCOMS), a system used to enhance patient involvement in mental health services and improve therapeutic alliance and treatment progress. **Student engagement** will be measured by the SRS. **Parent engagement** will be measured by the Therapeutic Alliance Scales for Caregivers and Parents. **Symptoms and functioning** will be measured using the ORS. Emotional and behavioral symptoms will also be measured by the Pediatric Symptom Checklist, 35-item version (PSC-35) which has well-established reliability and validity to assess and monitor progress of internalizing and externalizing symptoms for children ages 4-18. The Therapeutic Alliance Scales for Caregivers and Parents and the PSC-35 will be collected directly from parents/guardians over the phone at baseline and follow-up intervals.

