5.1.1 Data Collection

Data Sources. Data sourced for this study will include computerized and hard copy research records. Any hard copy research records will be scanned and saved electronically on a Yale secure server before shredding the paper copy. Data sources will include:

- (1) Quantitative data from clinician self-report surveys about **MBC acceptability, appropriateness, and feasibility** as well as **MBC use** every three months during implementation supports. Some qualitative feedback will also be solicited on the survey for clinicians to expand on any details the standardized measures of these implementation outcomes could not capture. (*Primary outcome variables*)
- (2) Quantitative data on **MBC use (clinician fidelity)** coded by chart review protocol, in which fidelity includes presence of SRS and ORS measures in the online BON/PCOMS system to approximate fidelity per clinician. (*Primary outcome variables*)
- (3) Quantitative data on proximal and distal **student engagement and functioning outcomes** collected by the clinician as part of the project, retrieved from medical records and/or the PCOMS system directly (SRS, ORS). (*Secondary outcome variables*)
- (4) Quantitative data on **parent engagement** and distal **student symptoms** collected by the study team as part of the project from parents over the phone (Therapeutic Alliance Scales, PSC-35). (*Secondary outcome variables*)
- (5) Tracking data on parent **recruitment, clinician attendance/engagement in implementation supports**. (*Implementation mechanisms*)

Data sources 1-4 above refer to primary and secondary outcomes of explicit focus in the analyses and are listed in the table below.

Table 1. List of Measures and Data Collection Methods

Outcome	Measure	Method	Reporter	Interval
MBC Acceptability (content, complexity, relative advantage)	Acceptability of Intervention Measure (AIM)	Online survey	Clinician	Pre-training 3M follow up 6M follow up 9M follow up
MBC Appropriateness (for setting, provider, students served)	Intervention Appropriateness Measure (IAM)			
Feasibility (for SMH practice)	Feasibility of Intervention Measure (FIM)			
MBC Use	Current Assessment Practice Evaluation - Revised (CAPER)			

MBC Attitudes	Attitudes toward Standardized Assessment – Monitoring and Feedback (ASA-MF)			
Implementation Determinants	MBC Feedback Form – Assess Barriers and Facilitators			Pre-training

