ORS/SRS Acceptability	Usage Rating Profile – Assessment (URP-A)			3M follow up 6M follow up 9M follow up
Fidelity (MBC Use)	Retrospective coding of PCOMS measures (SRS, ORS)	Chart review and/or BON system	Study Team	Monthly
Student Engagement	Session Rating Scale (SRS)			
Student Functioning	Outcome Rating Scale (ORS)			
Student Symptoms	Pediatric Symptom Checklist (PSC-35)	Phone	Parent	Baseline* 3M follow up 6M follow up 9M follow up
Parent Engagement	Therapeutic Alliance Scales for Caregivers and Parents			

**after clinician consent, near initial clinician training*

Secure Data Recording and Maintenance:

Online survey data will be maintained in the PI's Yale Qualtrics account, accessible only by members of the study team listed on the IRB protocol. Online survey data will be downloaded and maintained on secure Yale storage servers and networks (i.e., Yale Box, network drive). Clinicians will provide their identifying information (name, email address) when they consent as well as a secure 4-digit anonymous code. They will be asked to submit this same 4-digit code with each follow-up survey. This will ensure the study team can track individual clinician responses over time, but each survey is completed confidentially. A password-protected Excel file including clinician identifying information and 4-digit codes will be maintained on secure Yale storage servers and networks, accessible only to study team members.

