Chart review data may be in various formats depending on the format of documentation and storage systems at each district (study site). We only need basic information such as child diagnosis, date entered services, treatment goals, and number of sessions attended. We will also ask for their anonymous BON code so we can link those data (see below). Consistent with best practices in chart review methodology, we will work with each district to identify a "data extractor" at their site who can obtain the relevant data for students of consented parents within the requisite time frame and prepare them for the study team. Our team will provide a list of names of children based on parental consent obtained, as well as the data we are requesting. Once we receive the chart data, we will deidentify it with a unique study identifier and keep the list of linked study IDs to names in a separate password-protected file. We expect that the requested chart review material can be transferred in electronic format to our site at Yale, we will use Yale's secure file transfer system, save the material on our secure Yale storage server or network, and then complete the enter the services data for each child. These files will be saved on our secure Yale storage server and network and entered into a database.

BON/PCOMS system data (including the Outcome Rating Scale and Session Rating Scale) will be maintained in the Better Outcomes Now (www.betteroutcomesnow.com) secure online system. Clinicians enter these data directly into PCOMS using their own anonymous code for students. There are no identifiable information in PCOMS. Our study team will be the PCOMS trainers and also have administrative privileges in PCOMS to support MBC

implementation. In order to protect the confidentiality of parents consenting to the study, the study team will not share the names of consented families with clinicians in order to access their PCOMS data. Instead, we will use aggregate, deidentified PCOMS data at the clinician level to estimate MBC fidelity. This is a HIPAA-compliant site developed specifically for secure progress monitoring data entry and viewing my clinicians and their clients.

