5.3 Statistical Method

5.3.1 Statistical Design

Quantitative Analyses

Quality control checks of the data and examination of variable distributions will be performed prior to formal analysis. There are *three* types of outcomes: (1) clinician report of acceptability, appropriateness, and feasibility (implementation outcomes), (2) clinician use of MBC (also an implementation outcome, fidelity), and (3) student engagement, progress and outcomes (effectiveness of MBC). For (1) and (2), the primary analysis will be a multilevel growth model with time (Level 1) nested within clinician (Level 2) for each of the implementation outcomes as they are clinician self-reported on clinician surveys. We will examine linear change of time as a continuous measure as well as time by time transitions across the longitudinal intervals of data collection. Attitudes toward MBC and other

independent variables (e.g., clinician professional and demographic characteristics, consultation call attendance, school district) will be entered into the models to examine correlations. In particular, we hypothesize parallel growth between attitudes and use of MBC over time.

For (3) we will conduct a 3-Level multilevel growth model with time (Level 1) nested within student/parent reported outcome (Level 1) nested within clinician (Level 3). Models will be estimated for each parent-reported outcome (e.g., parent-reported engagement, parent-reported symptoms on the PSC-35). Independent variables that will be entered as covariates in these models include MBC implementation outcomes, with the specific hypothesis that MBC use will be predictive of positive engagement and symptom reduction.

Also, for (3), the ORS and SRS are assessed at each session, hence, a mixed effects regression model will be used that accounts for intra-student correlation across student sessions and clustering of students within clinician. The unit of analysis will be session, however in primary analyses, to avoid an overly complicated model, session will not be modeled as a fixed effect in the regression model for the mean. Fixed effects will include time (baseline and post MP assessment for MP1, 2, or 3) and treatment condition (i.e. whether the clinician's agency is under the intervention or control condition).

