5.3.2 Sample Size Considerations

We plan to enroll 50 SMH clinicians and up to 150 parents of children or adolescents with mental illness. The rationale for this sample size is based on having a large enough sample of clinicians trained that a range of implementation outcomes can be observed and described as pilot data for a larger-scale, fully-powered study. The rationale for the 150 students is based on our prior research in quality improvement and implementation research in schools, where it is more feasible to introduce a new practice to clinicians by telling them they can select a subset of their caseload for MBC implementation. We will outreach to students the clinician reports they are using MBC with. Selection of a subset of cases will involve a random selection of recently consented cases.

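### Hypothesis 3 ties MBC use to change in symptoms and functioning, but no listed model term clearly tests that: the ORS/SRS model has no use term, and the parent-reported models do not say how use enters

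*Combined protocol and SAP*

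**What the plan says.** Section 3.1 states Hypothesis 3 as "MBC fidelity and use will be positively associated with engagement and mental health symptom and functioning progress over time". The same section calls the pilot underpowered.

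For parent-reported outcomes (PSC-35 symptoms and parent alliance), section 5.3.1 plans a three-level growth model over time, student and clinician. Independent variables serve "as covariates in these models include MBC implementation outcomes, with the specific hypothesis that MBC use will be predictive of positive engagement and symptom reduction". No interaction with time and no baseline adjustment is named.

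For the session-by-session scales, section 4.2.2 assigns student engagement to the SRS and says that symptoms and functioning "will be measured using the ORS". Section 5.3.1 lists two fixed effects for that model. One is time, defined by an assessment labelled MP1, 2 or 3 that the documents do not explain. The other is whether the clinician's agency is under intervention or control.

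The form of the use variable is open. For BON fidelity, section 5.1.1 says: "Instead, we will use aggregate, deidentified PCOMS data at the clinician level to estimate MBC fidelity". The same section collects self-reported use "every three months during implementation supports", and Table 1 lists that survey at pre-training, 3, 6 and 9 months and fidelity coding monthly.

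On timing, section 4.1.1 says: "Baseline engagement and student outcomes will be collected after initial clinician training session". The Table 1 footnote places the parent baseline "after clinician consent, near initial clinician training". Section 5.3.2 adds: "We will outreach to students the clinician reports they are using MBC with".

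**The concern.** A hypothesis about progress needs a coefficient that measures change. There are two gaps.

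1. **ORS/SRS model.** No use or fidelity term is listed. Treatment condition cannot replace it: section 4.1.1 gives all clinicians the same supports, and student outcomes begin only after training. As written, the functioning and student-engagement parts of Hypothesis 3 are not tested.

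2. **Parent-reported models.** If use is one value per clinician, its main effect is a difference in level averaged over the calls, with the baseline call included. Clinicians who use MBC more may simply see students who start better or worse. If use varies over time, its main effect mixes differences between clinicians with changes within a clinician. Section 5.3.1 does not say which form applies.

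Section 5.3.1 states that the estimates and 95% intervals will inform the power analysis of a larger trial. A coefficient that is partly a baseline difference would give that trial an effect size that is not an effect on change.

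**Working it through.** The plan gives no effect size, SD, intraclass correlation or power for this analysis, so there is no figure of its own to reproduce. The check is algebra, then an illustration.

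**From the documents:** 50 clinicians and up to 150 parents (150/50 = 3 per clinician); calls at 0, 3, 6 and 9 months (mean 4.5).

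**Assumed:** baseline variances of 0.1 (clinician), 0.5 (student) and 0.4 (residual), total 1; use in SD units; slope effect b = -0.03 per month per SD of use, which is 9 x -0.03 = -0.27 SD at 9 months; baseline difference g per SD of use; random slopes either none, student SD 0.05 per month, or student and clinician SD 0.05 each; no dropout; two-sided 5% t-test on 48 df. Lower scores are better.

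**Step 1: what a single-value main effect estimates.** If the use effect at month t is g + b t, a model with time and use but no interaction estimates g + b t_w. With random intercepts only, t_w = 4.5. Fitting random slopes moves the weight earlier: t_w is about 3.5 with student slopes and 2.1 with both.

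**Step 2: real effect on change, g = 0, random-intercept fit.**
- Coefficient: 4.5 x -0.03 = -0.135.
- Variance of a clinician mean: 0.1 + 0.5/3 + 0.4/12 = 0.300. SE = sqrt(0.300/50) = 0.0775. Ratio -1.74; benefit detected in 40%.
- If slopes truly vary, the variance rises by 0.0025 x 4.5^2/3 = 0.017 (student) and a further 0.0025 x 4.5^2 = 0.051 (clinician). The SEs are 0.0796 and 0.0857, and detection is 38% and 34%.
- With random slopes fitted, simulated REML fits (1,000 runs each) gave 27%, 16% and 10% for the three slope settings.

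**Step 3: use by time in the same settings.** The sum of squared time deviations is 45.
- No slopes: SE = sqrt((0.4/3)/45/50) = 0.0077. Ratio -3.90; 97%.
- Student slopes: SE = sqrt((0.00296 + 0.00083)/50) = 0.0087; 92%.
- Both: SE = sqrt((0.00296 + 0.00083 + 0.0025)/50) = 0.0112; about 74%. Simulation gave 68%.

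**Step 4: no effect on change, students of high-use clinicians start 0.20 SD better.** The main effect has expectation -0.20. The ratios are -0.20/0.0775, -0.20/0.0796 and -0.20/0.0857, so benefit is declared in 72%, 69% and 63%. Simulation with slopes fitted gave 66-71%. Use by time stays at its nominal error rate.

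**Step 5: cancellation.** A worse start of 4.5 x 0.03 = 0.135 SD per SD of use brings the expected main effect to zero with random intercepts. With slopes fitted, a smaller difference suffices (3.5 x 0.03 = 0.105, or 2.1 x 0.03 = 0.063).

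**Step 6: time-varying use (800 simulated runs per setting).**
- Use rising linearly from zero, g = 0: plain main effect 77-98%; within-clinician deviation 74-95%; time-varying use by time only 2-3%.
- Use already at half its final level at the parent baseline, g = 0: plain main effect 51-79%; within-clinician deviation 71-90%.

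**Other assumptions.** With 0.3 SD more change by month 9, clinician intraclass correlation 0.05-0.15 and several slope variances, the single-value main effect rejects in 12-54% and use by time in 82-99% when there is no baseline difference.

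**The case against.** The best defence is that this is loose wording in an exploratory analysis. A growth model in which use predicts symptom reduction already signals an interest in slopes, entering a covariate does not exclude a slope predictor, and the listed fixed effects need not be exhaustive. That is fair, and it makes the point one of specification. It does not remove the point: the candidate models answer different questions, and the choice would be made after the data are seen.

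Four stronger readings are tempting and are not supported.

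- A reader might infer that the plan commits to one use value per clinician. It does not. The statement about clinician-level aggregation concerns BON fidelity and does not say one value over time. Table 1 has four use surveys and monthly fidelity coding, and pairing surveys with calls is a natural reading. On it, the plain main effect can perform well (step 6).
- A reader might take the low end of the detection range as what the plan would deliver. Figures near 10% require fitted random slopes, which section 5.3.1 does not mention. A random-intercept fit gives 34-40%.
- A reader might infer that the parent baseline must be paired with a pre-training survey. The synopsis and section 5.1 also mention a post-training survey, although Table 1 does not list it for use and section 5.2 counts four surveys. The matching is unresolved.
- A reader might require a change test for engagement. Sections 3.3 and 5.3.1 can fairly be read as an association with the level of engagement.

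**Conclusion.** The point holds as under-specification, with one plain omission. The omission is that the ORS/SRS model contains no use term, so two parts of Hypothesis 3 have no listed test. This does not depend on how use is coded or on any assumed number. For PSC-35 symptoms, whether the stated covariate answers the hypothesis depends on a choice that the plan leaves open. With a single clinician value it does not: detection is about 10-40% against 68-97% for use by time, and a 0.20 SD better start alone yields a declared benefit in about 63-72%. With time-varying use the answer depends on where use starts and whether it is linked to baseline.

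All percentages rest on assumed variances and effects and on no dropout. The consequence is a reported estimate that may not be the Hypothesis 3 quantity. It is not a missed power target, since the plan sets none. The change is worth making, but the stakes are limited: a secondary objective, a pilot, and results given as intervals.

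**What to change.** Amend section 5.3.1 as follows.

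- **ORS/SRS model.** Replace the MP-based time term and the condition term with time since the start of services or of MBC. Add MBC use and, for ORS functioning, use by time. Take self-reported use as the predictor here: section 5.1.1 defines BON fidelity as the presence of ORS and SRS scores, so the predictor would otherwise be the availability of the outcome.
- **PSC-35 symptoms.** Name the Hypothesis 3 test. Either use a clinician-level summary of use by time, with its main effect, or, if the three-monthly survey is time-varying, split use into the clinician's mean and the deviation from it, with visit as categories. State which survey is matched to the parent baseline call. Do not rely on time-varying use by time (step 6).
- **Engagement (parent alliance and SRS).** State whether the association tested is with level or with change.
- **Random slopes.** Include them where the model supports them. With about three students per clinician they should not be mandatory at both levels.

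The cost is a few model terms and an IRB amendment, which section 6.2 requires for any protocol change. No new data are needed. If use starts at zero, rises linearly and has no baseline link, the split has slightly less power than a plain time-varying main effect (74-95% against 77-98%). A summary of use over follow-up includes use after the earlier calls, so it supports association only, which is all that Hypothesis 3 claims.
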